CLINICAL STUDY PROTOCOL

PROTOCOL TITLE

**A DOUBLE BLIND, RANDOMIZED, PLACEBO CONTROLLED STUDY
TO EVALUATE EFFICACY AND SAFETY OF “VIRACIDE”
IN THE MANAGEMENT OF CORONA VIRUS DISEASE 2019 (COVID-19)**

**Protocol Number: NS-VC-CT01-20
Clinicaltrial.gov ID: NCT04596085**

STUDY SYNOPSIS

Title	A double blind, randomized, placebo controlled study to evaluate efficacy and safety of “ViraCide” in the management of corona virus disease 2019 (COVID-19).
Study Description	
This is a double blind randomized placebo controlled study will be conducted on 124 subjects, 50 years and older with mild or asymptomatic COVID-19. If symptomatic, symptoms are mild (cough, weakness, sore throat, low grade fever 38.50C, respiratory rate should not be more than 22 / min, resting SpO2 >95%, normal highly sensitive C-reactive protein (HS-CRP) (<10mg/L). There are no signs of dehydration, sepsis or shortness of breath.
 
The study will be conducted at two centers. There will be a screening visit at Day -4 followed by three visits at the center at Days 1, 7 and 15 and a follow-up visit on Day 28. All participants will be randomized to receive either ViraCide (investigational product) or matching placebo. All subjects will receive SOC therapy.
 
Note: If subject is discharged before Day 15 PI’s discretion as per patients health condition, then assessments scheduled for Day 15 will be carried out on the discharge day (as far as possible and those not performed will be noted on appropriate CRF page) and Day 15 visit will be done telephonically.

Investigational Product/Study drug	ViraCide softgels given per orally
Comparison product	Matching placebo of ViraCide softgels given per orally
Study Design	Double blind, randomized, placebo controlled study. Subjects will be randomized to the experimental and control groups in a 1:1 ratio. In each group 62 subjects will be recruited, a total of 124 subjects. Subjects of the experimental arm will receive treatment with Study Drug, ViraCide and SOC. The control group will receive matching placebo and SOC. The study consists of the stages of screening, therapy, observation. There will be no switching of subjects between the arms. Participants will receive Study drug or matching placebo for 14 days during the study.
Sample Size	124, including 10% dropouts

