Primary Endpoints	
1. TICI using NEWS Score [Time Frame: First treatment date up to discharge day (PI's discretion as per patients health condition)]
 
The median time in days from the start of treatment with the study drug / placebo to the persistent achievement of all of the following criteria:
 
 • Stopping a fever (which is defined as a decrease in axillary temperature below 37 ° C without the use of anti pyretic drugs); • Respiratory rate <22 /min; • Oxygen saturation (SPO2) > 95% when breathing in atmospheric air. Measured using pulse oximetry • Systolic blood pressure ≤200mmHg • Pulse rate 51-90beats/minute • Is conscious and alert 
[Note: Persistent achievement means the preservation of each of the criteria for at least 7days.]
 
2. TTIC using 7-point ordinal scale
 
3. Rate of progression to severe/critical COVID-19 disease based on NEWS score [Time frame: First treatment date up to 15days]
 
4. Rate of progression to severe/critical COVID-19 disease based on 7-point ordinal scale [Time frame: First treatment date up to 28days]
 
5. Time to COVID-19 nucleic acid testing negativity in oropharyngeal/nasal swab) [Time Frame: First treatment date up to 28days]

Secondary Endpoints	
 1. Incidence of ICU admissions [Time Frame: 28days] 2. Subject survival rate [Time Frame: 28days] 3. Incidence of mechanical ventilation due to COVID-19 infection [Time Frame: First treatment date up to 28days] 4. Change in clinical or laboratory assessment of comorbid condition [Time Frame: First treatment date up to 28days] 5. Percent of participants with worsening comorbid condition [Time Frame: First treatment date up to 28days] 6. Proportion of subjects in the treatment arm who had AE, SAE 7. Proportion of subjects in the placebo arm who had AE, SAE
Subject Selection Criteria	
Inclusion criteria
 
 1. 50 years or older

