	
 2. Both male and female subjects will be included 3. Positive oropharyngeal/nasal swab RT-PCR for Sars-Co- V2. Diagnosed not more than 2 days ago (diagnosis ≤ 2 days). 4. Either asymptomatic or have mild symptoms. Onset of symptoms within no more than 4 days. If symptomatic, symptoms are mild (cough, weakness, sore throat, low grade fever 38.50°C, respiratory rate should not be more than 22 / min, resting SpO₂ $>95\%$, normal highly sensitive C-reactive protein (HS-CRP) ($<10\text{mg/L}$). There are no signs of dehydration, sepsis or shortness of breath. 5. Chronic stable medical conditions: diabetes mellitus, or hypertension, or chronic heart disease. Under treatment and controlled by medication 6. Signed informed consent/or consent given through text message, WhatsApp or e-mail. 7. Ability to understand the requirements of the Research Protocol and follow the research procedures. 8. Subject should be willing to be managed in isolation wards 9. Negative pregnancy test (for female participants) 10. Adequate contraception for study duration 
Exclusion criteria
 
 1. Less than 50 years 2. With severe COVID-19 symptoms requiring immediate hospitalization 3. Investigator considers the subject unsuitable for ViraCide 4. History of symptoms of more than 4 days 5. COVID-19 diagnosed >2 days ago using oropharyngeal/nasal swab RT-PCR for Sars-Co-V2 6. History of cardiopulmonary resuscitation

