Visits of Assessment	
Screening and 3 visits and one telephonic follow-up
 
Screening Inclusion/Exclusion Criteria, Subject Inform Consent, Demography, Medical History, Physical Examination, Vital Signs, HIV; HBsAg; HCV; Hs-CRP; Pulse oximetry; NEWS scoring; 7- point ordinal scoring; Medication list review (medications being taken for comorbid conditions), Lab assessment; Urine analysis Note: Patients who do not meet the study inclusion exclusion criteria during screening should not be randomized into the study.
 
Day 1 Randomization, Vital Signs, Pulse oximetry, AE/SAE, Concomitant Medication, ViraCide/ Placebo treatment start, NEWS scoring; 7-point ordinal scoring
 
Day 7 Physical Examination, Vital Signs, AE/SAE, Concomitant Medication, ViraCide/ Placebo Compliance check, Pulse oximetry; NEWS scoring; 7-point ordinal scoring. (Note: If the subject is discharged on this day as per PI's discretion and patient's health condition then assessment scheduled for day 15 will be carried out on discharge day).
 
Day 15 Physical Examination, Vital Signs, AE/SAE, Concomitant Medication, ViraCide/ Placebo treatment end, RT-PCR for

	
Sars- Co-V2, Hs-CRP, Safety Lab Tests, Pulse oximetry; NEWS scoring; 7-point ordinal scoring, ViraCide/ Placebo Compliance check, Lab assessment including urine analysis
 
Day 28 Phone call follow up for time :
 
 • until negative RT-PCR for Sars-Co- V2, COVID-19 related mortality, • development of any COVID-19 symptom, • development of any worsening of comorbid condition; • Development of new AE/SAE; Resolution status of previous AE/SAEs 
Note: If subject is discharged before Day 15 on PI's discretion as per patients health condition, then assessments scheduled for Day 15 will be carried out on the discharge day (as far as possible and those not performed will be noted on appropriate CRF page) and Day 15 visit will be done telephonically.

Laboratory Investigations	
Screening: Recording RT-PCR- Sars-Co-V2 result; Urine pregnancy test; HIV; HBsAg; HCV; Hs-CRP; Hematology* + Biochemistry + Urine analysis*; ECG
 
Day 1: No labs
 
Day 7: No labs
 
Day 15: Oropharyngeal/nasal swab for PCR- Sars-Co-V2; Hematology* + Biochemistry + Urine analysis*; ECG; Serological biomarker: Hs-CRP

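### Primary endpoint 1 is a median time in days with a 7-day persistence rule, but its criteria are scheduled only at Days 1, 7 and 15, so only Day 1 or Day 7 can be confirmed

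*Protocol*

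**What the plan says.** Protocol, Study Synopsis, Primary Endpoints, item 1 defines the endpoint as "The median time in days from the start of treatment with the study drug / placebo to the persistent achievement" of six criteria: temperature without antipyretics, respiratory rate, SpO2 on room air, systolic pressure, pulse and consciousness. A note under that item adds: "Persistent achievement means the preservation of each of the criteria for at least 7days". SAP section 2 repeats both the definition and the note.

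The schedule is in two rows of the synopsis. Study Description: "There will be a screening visit at Day -4 followed by three visits at the center at Days 1, 7 and 15", with a Day 28 follow-up. Visits of Assessment: "Screening and 3 visits and one telephonic follow-up". Entries for the visits after treatment starts:

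- At the start of dosing, the entry is "Day 1 Randomization, Vital Signs, Pulse oximetry, AE/SAE, Concomitant Medication, ViraCide/ Placebo treatment start, NEWS scoring; 7-point ordinal scoring".
- At the one visit midway through dosing, it is "Day 7 Physical Examination, Vital Signs, AE/SAE, Concomitant Medication, ViraCide/ Placebo Compliance check, Pulse oximetry; NEWS scoring; 7-point ordinal scoring".
- At the last centre visit, it opens with "Day 15 Physical Examination, Vital Signs, AE/SAE, Concomitant Medication, ViraCide/ Placebo treatment end", followed in the same entry by pulse oximetry, NEWS and the 7-point scale.

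The Day 28 telephone contact covers PCR status, mortality, symptoms, comorbidity and adverse events. It lists no vital signs, SpO2 or NEWS. A subject discharged before Day 15 has the Day 15 assessments on the discharge day, as far as possible, and a telephone contact on Day 15.

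SAP section 5.2 compares TTCI between arms with a Mann-Whitney U test. It gives no rule for improvement that falls between visits or is never confirmed.

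**The concern.** An endpoint stated in days has to be measured at something near daily intervals. Here the gaps are 6 and 8 days. Subjects enter with mild or no symptoms of at most 4 days' standing, so much of the improvement may fall inside the first gap, where Day 2 and Day 6 look the same. The persistence rule then removes the last visit as a possible onset.

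At stake is the meaning of the first-listed primary endpoint. A reported median could only be Day 1, Day 7 or not reached. A true difference of a day or two could leave both arms with the same median, and the test loses some ability to detect it.

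**Working it through.** **Plan's own figure.** The documents give no number for this endpoint. The only computed figure is the sample size: 112 × 1.1 = 123.2, rounded up to 124, or 62 per arm. The 112 cannot be reproduced because no effect size is stated. I use its 56 completers per arm below.

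**Step 1: which onset days can be confirmed.** An onset day counts as confirmed if every scheduled assessment from that day shows all criteria met and those assessments span at least 7 days.

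| First seen met | Later assessment | Elapsed days | Inclusive days | Confirmable |
|---|---|---|---|---|
| Day 1 | Day 7 | 7 − 1 = 6 | 7 | inclusive count only |
| Day 1 | Day 15 | 15 − 1 = 14 | 15 | yes |
| Day 7 | Day 15 | 15 − 7 = 8 | 9 | yes |
| Day 15 | none | – | – | no |

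Under either count the set is Day 1 and Day 7. Day 1 means the criteria were already met when treatment started. So anyone who improves on treatment has one confirmable value, Day 7, standing for onset anywhere in Days 2–7. The 7-day hold is inferred from separate visits. Fever or desaturation between them would not be seen.

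**Step 2: early discharge.** A discharge assessment adds no new value. By elapsed days, discharge on Days 8–13 leaves only Day 1 confirmable, and discharge on Day 14 leaves Days 1 and 7. By inclusive count the second group starts at Day 13.

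**Step 3: daily recording for comparison.** With measurement still ending at Day 15, the latest confirmable onset is 15 − 7 = Day 8 (elapsed) or 15 − 6 = Day 9 (inclusive).

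**Step 4: power.** All distributions here are assumptions. Setup: 56 per arm, two-sided 5% Mann-Whitney, observation to Day 15, unconfirmed subjects tied at one worst value. Daily readings give onset Days 2–8. The visit schedule gives Day 7 for onset in Days 2–7. Subjects meeting the criteria at the start score Day 1 in both.

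| Assumed resolution times | Met on Day 1 | Visit schedule | Daily | Loss (points) |
|---|---|---|---|---|
| Lognormal, log SD 0.6, medians 4 vs 3 days | 0% | 40% | 66% | 26 |
| same, 5 vs 3.5 | 0% | 65% | 85% | 20 |
| same, 6 vs 4.5 | 0% | 50% | 66% | 16 |
| same, 7 vs 5 | 0% | 65% | 76% | 11 |
| same, 5 vs 3.5 | 30% | 16% | 30% | 14 |
| same, 5 vs 3.5 | 50% | 7% | 11% | 4 |
| Lognormal, log SD 1.0, 5 vs 3.5 | 0% | 30% | 44% | 14 |
| Exponential, 5 vs 3.5 | 0% | 29% | 32% | 3 |
| Exponential, control median 3, hazard ratio 1.75 | 30% | 12% | 22% | 10 |
| Exponential, control median 8, hazard ratio 1.75 | 50% | 7.6% | 8.5% | 0.9 |

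Repeat runs put the largest loss at about 27 points, so the range is about 1 to 27.

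**Step 5: reported medians.** Take log SD 0.6, medians 5 vs 3.5 days, nobody meeting the criteria on Day 1. The share scoring Day 7 is Φ(ln(6/5)/0.6) = 62% in one arm and Φ(ln(6/3.5)/0.6) = 82% in the other. Both exceed half, so both medians are Day 7. In simulation they were identical in 95% of trials.

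**The case against.** **Other sources may exist.** The protocol available is a synopsis and no CRF is included. Subjects are in wards ("Subject should be willing to be managed in isolation wards", Inclusion criteria, item 8), and SAP section 4 mentions an IP diary and patient files. A reader might infer that the criteria are never recorded between visits. The documents show only that they are not scheduled between visits. Equally, neither document makes a ward chart or diary a source for the criteria, so the plan as written still yields only the visit readings.

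**The power loss is uncertain.** A reader could take the first four rows of the table as the size of the problem, a firm loss of 11 to 26 points. The documents do not support that. Asymptomatic subjects are eligible and mild entry already requires SpO2 above 95%, so some subjects, number unstated, will meet all criteria on Day 1. With 30–50% doing so, power is poor even with daily readings, and the visit schedule is not the main cause.

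**Late onset is mostly not the schedule's fault.** One might blame the visit spacing for every onset in Days 8–15 that cannot count. Most of that comes from the 7-day rule combined with the end of measurement at Day 15. Daily readings would recover Day 8, or Days 8–9 by inclusive count, and no more.

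**Endpoint 2 differs.** The persistence note sits under item 1 only. TTCI on the 7-point scale shares the coarse schedule, but Day 15 is a possible value there.

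**Daily ward data are not a complete remedy.** Discharge before Day 15 at the investigator's discretion is expressly foreseen, and a subject who resolves on Day 3 and leaves on Day 7 has no 7-day run on the ward.

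All five points limit the size or reach of the concern. None changes Step 1.

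**Conclusion.** The concern stands for primary endpoint 1. Followed as written, the schedule cannot deliver a median time in days with a 7-day hold. For subjects with complete visits it separates already met at start, met by Day 7 and still met at Day 15, and not confirmed. This follows from the visit days and the persistence rule alone and needs no simulation.

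The cost in power is about 1 to 27 points over lognormal (log SD 0.6 or 1.0) and exponential times, 0–50% meeting the criteria on Day 1, and 56 per arm. It is largest when nobody meets the criteria on Day 1 and times vary little. No single figure within that range can be defended from the documents.

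Endpoint 2 is affected by the coarse spacing only, not by the Day 1 or Day 7 limit.

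**What to change.** Choose one of two routes and state it in both documents.

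(a) **Keep the time in days.** Where the isolation ward already charts them (an assumption to confirm with the sites), transcribe the six criteria, antipyretic use and the 7-point category to the CRF for each ward day. Define TTCI as the first day of a run of at least 7 days with all criteria met, and say whether days are counted as elapsed or inclusive. State that, with measurement ending at Day 15, onset after about Day 8–9 is unconfirmable, and whether it is treated as not achieved or censored. Give a handling rule for subjects discharged before completing a 7-day run. The cost is one daily CRF page, transcription and source verification. There is no new procedure if the charts exist. Values not captured during the stay may not be recoverable later.

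(b) **Drop the time in days.** If daily data cannot be had, replace the endpoint with the proportion meeting all criteria at Day 7 and still at Day 15, with a stated rule for early discharge. The chi-square test that SAP section 5.2 already uses for progression rates would serve. The cost is a less ambitious endpoint.

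Under either route, reconcile the endpoint's time frame. It ends at discharge in the protocol and at PCR negativity in the SAP.

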Study Population	
 • 50 years or older • Positive RT- PCR for Sars-Co-V2. • Either asymptomatic or have mild symptoms. Onset of symptoms within no more than 4days • With chronic stable medical conditions: Diabetes Mellitus, or Hypertension, or chronic heart disease.
Study Duration	Total study duration approximately 35 days Screening: 04 days Treatment duration: 14 days Follow-up: 14 days from end of treatment

Number of Sites	02 (two)
Treatment Duration	14 days
Treatment Arms	
Two treatment arms
 
 • Arm A: ViraCide softgels: 3 soft gels, two times every day after breakfast and dinner for 14 days+ SOC Therapy • Arm B: Placebo softgels: 3 soft gels, two times everyday after breakfast and dinner for 14 days + SOC Therapy
Purpose of the study	To study the effectiveness and safety of the Study Drug, ViraCide
	softgels by oral administration compared with placebo softgels in 50 years or older subjects with asymptomatic or mildly symptomatic coronavirus infection (COVID-19) and stable comorbidities.
Objectives	
Primary Objectives
 
1. To evaluate the efficacy of “ViraCide” in the management of mild COVID-19 disease
 
Secondary Objectives
 
1. To evaluate the safety of “ViraCide” in the management of mild COVID-19 disease

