	
Note:
 
*Hematology: Complete blood count (CBC); erythrocyte sedimentation rate (ESR)
 
*Biochemistry:
 
 • Random Blood Sugar, • Serum Creatinine • SGOT, SGPT • Alkaline Phosphatase • Bilirubin-Total/Direct/Indirect • Total Proteins/Albumin/Globulin/A:Gratio • Low density lipoprotein (LDL) Cholesterol(Direct) • LDH • Total Cholesterol • Triglycerides • High Sensitive C-reactive protein(HS-CRP) • BUN (Blood Urea Nitrogen) /Urea • Serum Calcium • Serum Sodium • Serum Potassium • Uric Acid 
*X-ray PA view is an optional test at screening. It may be done

	
at any other time during the study if deemed necessary by the Investigator
 
*Urine pregnancy test (for females only) at screening
 
Note: If subject is discharged before Day 15 PI's discretion as per patients health condition, then assessments scheduled for Day 15 will be carried out on the discharge day (as far as possible and those not performed will be noted on appropriate CRF page) and Day 15 visit will be done telephonically.

Standard of Care Therapy	
SOC therapy for coronavirus infection (COVID-19, SARS-CoV-2) has not been developed yet. Treatment will be given as per the discretion of the PI or as per the guidelines issued by the GOI. GOI guidelines can be accessed here: https://www.mohfw.gov.in/

Concomitant Medications Allowed by the Protocol	
 1. Medications for Diabetes Mellitus 2. Medications for hypertension 3. Statins 4. Blood thinners like aspirin at PI discretion 5. Any medication deemed necessary by the PI to manage the AE/SAE 6. Any other medication deemed necessary by the PI to manage a comorbid condition that is not likely to affect the treatment Protocol
Prohibited Concomitant Medications	Any other herbal medicine or dietary supplement
Statistical Analysis	
Sample size of total 112(56 cases in each arm) completed cases needed to assess the study objective at 80% power and 5% level of significance.
 
Considering 10 % dropout total 124 (62 cases in each arm) cases will be enrolled in this study.

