5.4 Safety Analysis

Incidence and rate of adverse events.

AEs and SEs will be summaries counting both the number of separate events and the number of subjects experiencing events occurring during the study period will be provided overall, per system organ class and preferred term by presenting.

Confidential & Proprietary

the unauthorized use, disclosure, distribution or copying of these information is strictly prohibitea

Furthermore, similar summaries will be provided stratified according to the seriousness, severity, and relationship to the study medication. The percentage of cases with an event will be analyzed and compared by the Chi-Square test. Mean changes in in vital signs and Laboratory variables, will be assessed by using student t-test for with in groups and analysis of variance for comparison between groups.

6. Listing of Tables

- Participant Disposition
- Demographical and baseline characteristics with comparison of demographical and baseline characteristics
- Profile of Medical History and clinical Examinations
- Changes in Vital Signs
- Comparison of Mean Time to Clinical Improvement (TTCI) using NEWS Score
- Comparison of Mean Time to Clinical Improvement (TTCI) using 7 point ordinal scale.
- Rate of progression to severe/critical COVID-19 disease based on NEWS score [Time frame: First treatment date up to 28 days
- Rate of progression to severe/critical COVID-19 disease based on 7point Ordinal scale [Time frame : First treatment date up to 28 days

Confidential & Proprietary

The unauthorized use, disclosure, distribution or copying of these information is strictly prohibited

- Mean Time to COVID-19 nucleic acid testing negativity in oropharyngeal/nasal swab) [Time Frame: First treatment date up to 28 days]
- Incidence of ICU
- Profile of subject survival rate
- Incidence of Mechanical ventilators
- Time to COVID-19 nucleic acid testing negativity in oropharyngeal/nasal swab) [Time Frame: Days 1, 7, 15]
- Percent of participants with worsening comorbid condition [Time Frame: First treatment date up to 28 days]
- Changes in clinical assessment of co morbid conditions
- Comparison of Changes Laboratory Variables
- Profile of adverse events in each group
- Profile of Serious adverse events in each group

7. Graphs

Individual Graphs for all Primary and secondary variables

8. Software

SPSS Version 10.0

Confidential & Proprietary

The unauthorized use, disclosure, distribution or copying of these information is strictly prohibited

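### Random blood sugar is the only named glycaemic test and neither draw has a meal condition, which adds avoidable noise to the glucose and triglyceride comparisons

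*Protocol*

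**What the plan says.** The list of biochemistry tests in the protocol synopsis (Laboratory Investigations) contains "Random Blood Sugar" and triglycerides. It names no fasting glucose, post-prandial glucose or HbA1c.

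Biochemistry is drawn twice. The screening list includes "Hs-CRP; Hematology* + Biochemistry + Urine analysis*; ECG", and the second draw is given as "Day 15: Oropharyngeal/nasal swab for PCR- Sars-Co-V2; Hematology* + Biochemistry + Urine analysis*; ECG". Days 1 and 7 have no laboratory tests. For subjects discharged early, "then assessments scheduled for Day 15 will be carried out on the discharge day", as far as possible. Day 28 is a telephone contact that asks, among other things, about "development of any worsening of comorbid condition", so it yields no glucose value. No fasting state, time since the last meal or clock time is given for either draw.

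Two planned analyses can use these values:

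- Diabetes is one of three qualifying comorbidities, and protocol secondary endpoint 4 is "Change in clinical or laboratory assessment of comorbid condition".
- SAP 5.4 says that mean changes in vital signs and "Laboratory variables, will be assessed by using student t-test for with in groups", with analysis of variance between groups. No covariate for meal or sampling time is named.

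**The concern.** A random glucose reading depends on how long ago the subject ate. Each change score therefore contains two meal intervals that the plan does not control, in addition to any real change in glycaemic control. Triglycerides from the same sample are exposed in the same way.

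In a blinded, randomised comparison this is noise rather than bias: it widens the SD of change in both arms and lowers the chance of seeing a real difference. The within-group t-tests lack that protection. If screening samples tend to be drawn at a different time of day from Day 15 or discharge samples, an arm can show a mean change that reflects the clock. At stake is how much a null glucose result can be trusted, in a trial that enrols people with diabetes and sets out to follow their comorbidity.

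**Working it through.** **Plan's own figure.** The documents give no number for glucose, so there is none to reproduce. The only relevant count is the sample size: 56 completers per arm, enlarged to 62. It reproduces as 56 × 1.10 = 61.6, rounded up to 62.

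**Inputs**

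- From the protocol: 56 completers and 62 enrolled per arm; 80% power and 5% significance (taken as two-sided, which is not stated).
- Assumed, because the documents are silent: half of completers diabetic, 56 / 2 = 28 per arm; within-subject SD of 20 to 30 mg/dL under standardised sampling and 40 to 60 mg/dL at random times; a true between-arm difference in change of 20 mg/dL.

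**Formulas**

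- SD of change = within-subject SD × √2.
- Standardised difference d = 20 / SD of change.
- Power from the two-sample t test with n per arm.

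**Results**

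| Within-subject SD (mg/dL) | SD of change (mg/dL) | d | Power, n = 28 | Power, n = 62 |
|---|---|---|---|---|
| 20 (standardised) | 28.3 | 0.71 | 74% | 97% |
| 30 (standardised) | 42.4 | 0.47 | 41% | 74% |
| 40 (random) | 56.6 | 0.35 | 26% | 50% |
| 60 (random) | 84.9 | 0.24 | 14% | 26% |

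The column for 28 illustrates the diabetes component of endpoint 4. The column for 62 illustrates the SAP 5.4 comparison in all subjects; it is an upper limit, since it assumes that everyone enrolled gives both samples. At n = 62 the difference detectable with 80% power is about 29 mg/dL at SD 40 and 43 mg/dL at SD 60.

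**Sensitivity to the diabetic share.** With one third or two thirds of 56 diabetic (19 or 37 per arm), power at SD 20 is 56% or 85%, and at SD 40 it is 19% or 32%. The loss appears at each share.

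**Sensitivity to the amount of meal noise.** Let s be the SD of change under standardised sampling and m the meal-timing SD of one reading. Two readings give SD² = s² + 2m². Suppose standardised sampling had 80% power (normal approximation):

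| m / s | Power | Factor on N, 1 + 2(m/s)² |
|---|---|---|
| 0.25 | 75% | 1.1 |
| 0.5 | 63% | 1.5 |
| 1 | 37% | 3.0 |
| 2 | 15% | 9.0 |

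The loss is thus slight to severe, depending on a ratio that the documents do not give.

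**The case against.** The strongest reply is that neither document makes random glucose the diabetes variable. Endpoint 4 allows a clinical or a laboratory assessment. SAP 5.3 speaks of changes in clinical comorbid conditions, and the SAP table list keeps the clinical comorbidity assessment apart from the laboratory changes. Worsening diabetes could also surface through concomitant medication, adverse events or the Day 28 call. This stands. A reader might infer that a real worsening would probably be missed and reported as no change; the documents do not support that. The undefined comorbidity variable and worsening threshold are a more basic gap, which fasting samples would not close.

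Second, a reader might call the glucose safety comparison nearly uninformative. That would apply the power of a diabetic subset to an analysis of all subjects. With up to 62 per arm and SD 40, power for 20 mg/dL is 50%, which is reduced precision and no more.

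Third, a reader might say that meal time goes unrecorded. The documents are only silent: the protocol text here is a synopsis, no CRF is shown, and SAP section 4 has source documents, the product diary and laboratory reports feeding the CRF.

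Fourth, an obligatory fasting screening sample has a price. Diagnosis must be no more than 2 days old and symptoms no more than 4 days old, so waiting until next morning could cost eligibility. Discharge-day samples follow a discretionary decision and cannot always be taken before breakfast. This stands too, and it limits the fix.

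What survives is that no meal condition is specified, the SAP names no adjustment, and both can be improved without another sample.

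**Conclusion.** The point holds as a minor, inexpensive improvement. The facts are firm: one named glycaemic test, two scheduled draws, no meal condition, no adjustment. The consequence is lower precision for the laboratory part of the diabetes component of endpoint 4 and for glucose and triglycerides in SAP 5.4, plus a risk of misleading within-group tests if draw times shift between visits. Between-arm bias does not follow, and no primary endpoint is affected.

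The size is illustrative. Every SD, the diabetic share and the 20 mg/dL difference are assumed, and the contrast narrows if standardised sampling is itself noisy: at n = 28, power is 41% at a standardised SD of 30 against 26% at a random SD of 40. The diabetic subset is small under any sampling rule.

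**What to change.** 1. **CRF:** record hours since the last meal at both glucose draws (screening, and Day 15 or discharge).
2. **SAP 5.4, and the laboratory part of endpoint 4:** compare the arms on Day 15 or discharge-day glucose and triglycerides in a model with the screening value and the time since the last meal at each draw as covariates. Because the second meal interval is recorded after randomisation, show the unadjusted comparison beside it.
3. **Protocol, Laboratory Investigations:** take both samples before breakfast where this delays neither enrolment, given the 2-day diagnosis and 4-day symptom limits, nor discharge. Subjects are managed in isolation wards and the product is taken "two times every day after breakfast and dinner for 14 days", so a pre-breakfast sample on the ward would also make the interval from the last dose more uniform.

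The cost is one extra CRF field, completed at two draws, with no additional sample. Some draws will remain non-fasting, and time since the last meal will not capture what was eaten, so part of the noise stays.
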